8.2 Sample Processing

EDTA tubes will be processed to obtain double-spun plasma and peripheral blood mononuclear cells (PBMCs); serum tubes will be processed to obtain serum.

8.3 Planned Correlative Studies

8.3.1 Monitoring anti-SARS-Cov2 antibody responses in Duvelisib-treated COVID-19 patients

Rationale of the study

The production of neutralizing antibodies represents an important host defence mechanism against systemic dissemination of SARS-CoV2. Our understanding of the molecular determinants controlling in B cells the strength and quality of the antibody response against SARS-CoV2 during the acute phase of infection remains largely unknown. Also, we have limited information on the molecular effectors that control in B cells the production of specific classes (ie. IgM, IGG, IGA) and subclasses (IGG1, IGG2, IGG3, IGG4) of antibodies during SARS-CoV2 infection. The latter information is crucial to understand which factors trigger the production of antibody classes and subclasses with neutralizing activity rather than those exerting pro-inflammatory functions by binding to Fc receptors on macrophages and natural killer cells, or by complement fixation. Finally, the identification of molecular determinants contributing to the establishment of long-lived antigen-specific memory B cells and antibody-secreting plasma cells during the acute phase of SARS-Cov2 infection represents a key step to possibly modulate the duration of anti-viral responses.

PI3K signalling is a strong candidate for controlling key functions of B cells related to the production of antigen-specific antibodies during both T-cell dependent and independent anti-viral immune responses. Therefore, Duvelisib inhibition of PI3K catalytic function offers the opportunity to understand whether such treatment can influence the quality and quantity of the antibody response raised against SARS-CoV2 during the acute phase of the infection. Specifically, Duvelisib may influence the extent of B cell activation in response to SARS-CoV2 recognition, by modulating B cell receptor (BCR) signalling, which in turn controls B cell proliferation and terminal differentiation [16,17]. Duvelisib exposure may also influence immunoglobulin isotype switching [17] This effect may lead to a substantial shift in the classes and subclasses of antibodies produced during the viral infection. In particular, Duvelisib treatment may change the ratio between neutralizing IGG1 antibodies and pro-inflammatory IGG3 antibodies produced during the acute phase of SARS-CoV2 infection. Duvelisib interference of PI3K signalling may enhance the process of antibody somatic hypermutation in antigen-specific B cells recruited into germinal centers (GC), in the frame of a conventional T-cell dependent anti-SARS-Cov2 immune response [17]. Whether enhanced antibody diversification ignited in GC B cells by Duvelisib, positively impacts on the average affinity of antibodies raised against SARS-Cov2 remains to be determined. Finally, Duvelisib treatment, during the acute phase of SARS-Cov2 infection, could exert a crucial impact on the net output of germinal centers represented by the generation of long-lived memory B cells and plasma cells producing high-affinity anti-virus antibodies [17,18].

Aim of the investigations and experimental plan

The proposed studies aim to obtain a comprehensive understanding of the effects of Duvelisib treatment on the antibody response raised against SARS-CoV2 in the acute phase of infection. Specifically, we will measure the effects of Duvelisib treatment on the concentration of all classes (IGM, IGG, IGA) and subclasses (IGG1, IGG2, IGG3, IGG4), IGA1 and IGA2) of serum anti-SARS-CoV2 Spike RBD-specific antibodies, respectively at Day-2, Day-4, Day-8, Day-15, and Day-29 of infection. Through serum neutralization tests, we will also estimate at the same time points, the effects of Duvelisib on the extent of production of anti-SARS-Cov2 neutralizing antibodies. Finally, flow cytometric determinations will establish whether Duvelisib treatment impacts. on the frequency of circulating RBD-binding long-lived CD27⁺ IgM- and Ig-switched memory B cells and CD38⁺CD138⁺ plasma cells/plasma blasts, assessed at the different time points after the infection.

Methods

The laboratory of Dr [name] (The FIRC Institute of Molecular Oncology, IFOM, Milan) has developed an in-house ELISA-based serological assay to measure serum/plasma levels of the entire spectrum of antibody classes and subclasses (IGM, IGG1, IGG2, IGG3, IGG4, IGA1/A2) raised against the Receptor Binding Domain (RBD) of the SARS-CoV2 Spike protein, produced in recombinant fashion. In particular, the assay will ensure the measurement of absolute amounts

(i.e concentration) of IGM- and IGG1-specific anti-RBD antibody titers. An ELISA-based competition assay will be employed to quantify the neutralizing activity of the serum of SARS-Cov2-infected patients. To perform the serological tests mentioned above, we will need between 0.5 and 1.0 ml of fresh or -20°C - stored serum (or plasma). One-two ml of fresh or cryopreserved peripheral blood mononuclear cells will be needed to estimate by flow cytometry the frequency of antigen-specific memory B cells and plasma cells revealed after staining the cells with a tetramer form of fluorescent labelled recombinant RBD.

8.3.2 Additional analyses

Analysis will include, but are not limited to, the evaluation of cytokine expression via multiplex cytokine array or other markers/predictors of response.

9.0 DATA SUBMISSION SCHEDULE

Case Report Form	Submission Schedule
Original Consent Form	Prior to registration
Registration Form Eligibility Form Medical History Form Treatment History Form Medical Assessment Form Lab Form	At Baseline
Medical Assessment Form Lab Form	As Scheduled in Section 7.0
28 Day Overall Survival Form	At Day 28 or Death
Adverse Events	Continuous from baseline through safety follow-up visit
MedWatch Form	See Section 10.0 for reporting requirements
SAE / CIOMS Form	See Section 10.0 for reporting requirements for Canada
End of Treatment Form	At the completion of study follow-up
Death Form	At time of death

Any queries generated by Washington University must be responded to within 28 days of receipt by the participating site. The Washington University research team will conduct a regular review of data status at all secondary sites, with appropriate corrective action to be requested as needed.

10.0 REGULATORY AND REPORTING REQUIREMENTS

The entities providing oversight of safety and compliance with the protocol require reporting as outlined below. Please refer to Appendix C for definitions and Appendix D for a grid of reporting timelines.

Adverse events will be tracked from start of treatment through Day 29. All adverse events must be recorded on the toxicity tracking case report form (CRF) with the exception of:

- Baseline adverse events, which shall be recorded on the medical history CRF

Refer to the data submission schedule in Section 9 for instructions on the collection of AEs in the EDC.

Reporting requirements for Washington University study team may be found in Section 10.1. Reporting requirements for secondary site study teams participating in Washington University-coordinated research may be found in Section 10.2.

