Study Description:	Patients with a diagnosis of COVID-19 with critical disease manifestations will be randomly assigned to receive duvelisib or placebo
Objectives:	
Primary Objective: To evaluate the efficacy of duvelisib for the treatment of COVID-19 disease manifestations.
 
Secondary Objectives: To evaluate the safety and tolerability of duvelisib for the treatment of COVID-19 disease manifestations.

Endpoints:	
Primary Endpoint:
 
 • 28 day overall survival 
Secondary Endpoints:
 
 • Hospital and ICU length of stay • Duration of ventilator • Duration of vasopressors • Duration on renal replacement therapy • Viral kinetics • Adverse Events
Study Population:	Twenty-eight patients (approximately 14 per arm) over the age of 18 with a diagnosis of COVID-19 with advanced disease manifestations including one or more of the following: extensive lung involvement, respiratory failure, shock, or cardiac dysfunction.
Phase:	Pilot Phase 2
Description of Sites/Facilities Enrolling:	This is a multi-center study open at Washington University School of Medicine and Missouri Baptist Medical Center.
Description of Study Intervention:	Patients will receive either duvelisib 25mg or placebo for 10 days. Both participants and researchers will be blinded.
Study Duration:	18 months
Participant Duration:	6 months

Table of Contents

PROTOCOL SUMMARY	4
1.0 BACKGROUND AND RATIONALE	7
1.1 COVID-19 and Cytokine Release Syndrome	7
1.2 Lessons and Preclinical Data from CART-related CRS	7
1.3 Gene edited CART model for the Mitigation of CRS	8
1.4 PI3K Inhibition Potently Mitigates CRS in Pre-clinical CART Model.....	9
1.5 PI3K Inhibition to Mitigate Pathogenesis of Advanced COVID-19	10
2.0 OBJECTIVES	11
2.1 Primary Objective	11
2.2 Secondary Objectives.....	11
2.3 Objectives and Endpoints Table	11
3.0 PATIENT SELECTION	12
3.1 Inclusion Criteria	12
3.2 Exclusion Criteria	13
3.3 Inclusion of Women and Minorities	13
4.0 REGISTRATION PROCEDURES	13
4.1 Confirmation of Patient Eligibility	13
4.2 Screen Failures.....	13
5.0 STUDY TREATMENT	14
5.1 Overview.....	14
5.2 Dose Modifications.....	14
5.3 Supportive Care	15
5.4 Viral Load Monitoring.....	17
5.5 Worsening COVID-19 Symptomology	17
5.6 Duration of Therapy.....	17
5.7 Duration of Follow-up	18
5.8 Lost to Follow-Up.....	18
6.0 PHARMACEUTICAL INFORMATION.....	18
6.1 Duvelisib.....	18
7.0 SCHEDULE OF ASSESSMENTS.....	20
8.0 CORRELATIVE STUDIES	22

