5.7 Duration of Follow-up

All patients will be followed as according to the protocol calendar in Section 7.0 for the duration unless the patient withdraws consent or is lost-to-follow-up. Following the safety follow-up visit, patients will continued to be monitored for survival and late-onset toxicity every 3 months for up to 6 months. For these long-term follow-up visits, a telephone visit can be made in lieu of a physical visit.

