10.1.2 Reporting to Verastem

All initial and follow-up SAEs to include unanticipated problems and pregnancies, must be reported to Verastem, Inc. Safety and Pharmacovigilance via PPD at [contact] within 24 hours of knowledge of the event concerning the Verastem, Inc. product. Reports should be submitted in English via the sponsor-investigator internal SAE/pregnancy forms, MedWatch or CIOMS forms.

Pregnancy per se is not considered an AE unless there is cause to believe that the study interventions may have interfered with the effectiveness of a contraceptive medication or if the outcome of the pregnancy meets SAE criteria (miscarriage or congenital anomaly/birth defect, etc.), in which case it should be reported in the same manner and timelines as an SAE. In addition, any infant death or congenital anomaly occurring after 30 days that the Investigator suspects is related to the in-utero exposure to the study interventions should also be reported as an SAE. Hospitalization for normal delivery of a healthy newborn is not an SAE.

Since duvelisib has not been evaluated in pregnant or nursing women, the treatment of pregnant women or WCBP who are not using highly effective contraception is contraindicated.

Pregnancies occurring in subjects or partners of male subjects during the study intervention period and until 30 days after the subject's last dose of study interventions are considered immediately reportable events. If a pregnancy occurs in a subject, study interventions must be discontinued immediately. The pregnant woman should be referred to an obstetrician/gynecologist experienced in reproductive toxicity for further evaluation and counseling. The Investigator will observe the pregnant woman until completion of the pregnancy and must notify Verastem of the outcome within 24 hours of the Investigator's knowledge of the pregnancy outcome using a Pregnancy Outcome Form. This notification includes pregnancies resulting in live, "normal" births.

SAE reports must contain the following minimum information:

- At least one identifiable reporter
- One single identifiable patient
- At least one suspect adverse reaction
- At least one suspect medicinal product
- The sponsor-investigator's assessment of causality for the event

All such occurrences listed in this section shall be reported to Verastem using an approved local regulatory form and/or SAE form provided by Verastem and sent by facsimile or email to the following:

[contact]

Email: [contact]

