12.2 Statistical Analysis Plan

The primary endpoint is 28 day overall survival (OS) and will be treated as a binary outcome for the purposes of the primary analysis and will be described using descriptive statistics with the corresponding 95% confidence intervals. This will be an intent-to-treat analysis, and all patients randomized will be included in the analysis. The assumption is that all patients will be followed for at least 28 days. Patients who are lost to follow-up for any reason prior to this point will be included in the analysis and considered treatment failures and treated the same as a death. The 28 day OS of each cohort, duvelisib versus placebo, will be compared using Fisher's exact test of independence.

In addition to the primary analysis, OS will be treated as a time-to-event variable and will be described using Kaplan-Meier product limit estimators of event time curves and, if reached, medians with 95% confidence intervals. Cox proportional hazards models may be used to adjust for potential confounding effects. These analyses are considered exploratory, and we acknowledge that the proposed sample size will have low power for such adjustment.

The analyses of secondary end points are all exploratory in nature. Secondary endpoints of efficacy include: hospital and ICU length of stay and duration of ventilator (for those on a ventilator at the time of randomization), vasopressors, and renal replacement therapy. Kaplan-Meier product limit estimators of event time curves and, if reached, medians with 95% confidence intervals, and compared between cohorts using the Log-Rank test. For these analyses, patients will be censored at Day 28 or at death, whichever is earlier. Secondary end points of toxicity are viral kinetics and adverse events. The rate of viral load elevation and other adverse events of interested will be summarized using descriptive statistics and compared using Fisher's Exact tests.

Demographic and clinical characteristics of the sample and of each cohort will be summarized using descriptive statistics. For continuous variables, the number of patients, mean, standard deviation, median, minimum, maximum, and quartiles will be provided. For categorical variables, the number and percent of patients in each demographic/characteristic category will be summarized with 95% confidence intervals.

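### Late-onset toxicity is to be monitored to six months, but routine adverse event recording ends at Day 29 and no systematic by-arm record after that is specified

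*Combined protocol and SAP*

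**What the plan says.** Section 5.7 (Duration of Follow-up) sets a safety purpose for the period after the safety follow-up visit: "patients will continued to be monitored for survival and late-onset toxicity every 3 months for up to 6 months". It adds that "For these long-term follow-up visits, a telephone visit can be made in lieu of a physical visit". The Protocol Summary gives "Participant Duration: 6 months".

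The collection rules stop earlier. Section 10.0 says "Adverse events will be tracked from start of treatment through Day 29" and then hands the detail over: "Refer to the data submission schedule in Section 9 for instructions on the collection of AEs in the EDC". In Section 9.0 the submission schedule for adverse events is "Continuous from baseline through safety follow-up visit". In the Section 7.0 grid the last safety follow-up column is Day 29, and no column follows it.

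The analysis is in Section 12.2: "The rate of viral load elevation and other adverse events of interested will be summarized using descriptive statistics and compared using Fisher's Exact tests". It gives no time window and does not mention late-onset toxicity.

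**The concern.** Two rules end adverse event collection at the point where a third section starts a further safety observation. A site that follows all three would ask patients about late toxicity at about three and six months and have no designated place to record a non-serious answer.

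Safety and tolerability is the secondary objective, and the table in Section 2.3 lists adverse events as one of its two endpoints. Section 12.0 says the study is meant to generate hypotheses on toxicity as well as efficacy. If late events are noted by some sites in clinic records, reported by others as serious events, and left unrecorded elsewhere, the trial cannot give a consistent account by arm of what happened after Day 29, although it plans the contacts that would supply one.

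**Working it through.** The protocol states no figure on this point, so there is none to reproduce. The check compares the sections and then measures the uncovered period.

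**Step 1. Does another section supply the missing record?**

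- *Section 7.0 grid.* It has no month 3 or month 6 column. The Medical Assessment and Lab Forms are submitted on the Section 7.0 schedule, so they stop at Day 29 as well.
- *Section 9.0, other forms.* The Death Form covers late deaths. The End of Treatment Form is due when follow-up is complete, but no toxicity content is given for it. The MedWatch and SAE/CIOMS forms refer to the Section 10.0 reporting rules.
- *Section 10.1.2.* "All initial and follow-up SAEs to include unanticipated problems and pregnancies, must be reported to Verastem", with no end date in that sentence. A late serious event could travel this way. The route leads to the supplier's pharmacovigilance group and is not linked to the by-arm comparison.
- *Section 10.3.* Events outside expedited reporting must also go into the EDC, and no window is given. Section 10.0, however, makes Section 9.0 the governing rule for adverse events in the EDC, and Section 9.0 stops at the safety follow-up visit.
- *Section 11.0.* Reports to the DSMB continue only while patients are on active treatment. With dosing of up to 10 days, toxicity at three or six months in the last patients enrolled need not reach the board.
- *Section 12.2.* No late-toxicity analysis is planned.

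Serious events and deaths therefore have partial routes. Systematic collection of late toxicity in both arms has none.

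**Step 2. How long is the uncovered period?**

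Inputs: recording ends at Day 29 (Section 10.0); last dose no later than Day 10 if dosing is uninterrupted (Sections 5.1 and 7.0); follow-up of six months, taken as 365.25 / 2 = 182.6 days. The documents leave open when the six months start, so both readings are shown.

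- Six months from the start of treatment (the Protocol Summary's participant duration): share recorded = 29 / 182.6 = 15.9%; not recorded = 182.6 − 29 = 153.6 days.
- Six months from the Day 29 visit (the wording of Section 5.7): total = 29 + 182.6 = 211.6 days; share recorded = 29 / 211.6 = 13.7%; not recorded = 182.6 days.
- Recording after a Day 10 last dose: 29 − 10 = 19 days.

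**Step 3. Do the sections agree on other limits?**

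- Pregnancies are reportable until 30 days after the last dose (Section 10.1.2 and Appendix D). After a Day 10 last dose that is Day 10 + 30 = Day 40, so part of Section 10 already looks beyond Day 29.
- The start of the window also differs: Section 9.0 begins at baseline, Section 10.0 at the start of treatment.

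**The case against.** The strongest reply is that nothing in the protocol tells anyone to throw a late event away. The supplier reporting rule and the EDC rule for non-expedited events carry no end date, and the Fisher comparison has no window that would exclude a late event already on file. This stands. A reader might infer that late toxicity is barred from the safety analysis, and the documents do not go that far. What they lack is a scheduled form and contact that would collect it in the same way for every patient.

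A reader might also infer that the cut-off flatters duvelisib. The same Day 29 limit applies to both arms of a randomised, blinded trial, and late events on placebo go unrecorded too. The protocol gives no timing of toxicity by arm, so incompleteness is supported and a direction of bias is not.

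It is tempting to apply the rates in Section 6.1.7 (18% for serious or fatal diarrhoea or colitis, 5% for pneumonitis) to 14 treated patients and call the result the likely loss. Those rates come without exposure length or onset time, this trial doses for at most 10 days, and Section 2.3 itself says it is unclear whether similar events will be seen in this population. Nor would such a product count events after Day 29.

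Finally, the study is a 28-patient pilot, and Section 12.2 calls all secondary analyses exploratory. Even two late events against none would not give a significant comparison: two-sided Fisher p = 2 × C(14,2) / C(28,2) = 2 × 91 / 378 = 0.48. This limits the importance of the point for testing. It has less force for description, because one patient is 1/14 = 7.1 percentage points of an arm.

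**Conclusion.** The conflict between Section 5.7 and Sections 7.0, 9.0 and 10.0 is real. As written, a safety observation that the protocol plans has no systematic record by arm, and the adverse event comparison in Section 12.2 would be incomplete after Day 29. The recorded window is 29 days, or 14% to 16% of planned follow-up, with 154 to 183 days beyond it. That share is calendar time and not risk, since the window covers an uninterrupted 10-day course plus 19 days. The size and direction of any effect on the toxicity comparison cannot be determined from the documents.

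The conclusion assumes that the safety follow-up visit in Sections 5.7 and 9.0 is the Day 29 column of the grid, which agrees with Section 10.0. The primary endpoint is untouched. This is a worthwhile, inexpensive improvement to the safety objective.

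**What to change.** Reconcile Sections 5.7, 7.0, 9.0, 10.0 and 12.2:

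- *Section 7.0:* add the two long-term contacts as columns and state the date from which they are counted.
- *Sections 9.0 and 10.0:* extend adverse event recording to those contacts for at least serious and treatment-related late-onset events, on a short form. Align the start of the window in the two sections at the same time.
- *Section 12.2:* state the window. Report events by arm to Day 29 and, descriptively, to six months, with the number of patients contacted in each arm.

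The minimum alternative is to state that late toxicity will not be collected for analysis. That removes the contradiction but gives up information from contacts that will take place anyway.

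The cost is a short CRF at each planned contact (at most 2 × 28 = 56 forms, fewer after deaths), which can be completed by telephone, plus a protocol amendment, an EDC change and one additional descriptive table. No dose or clinical rule changes.

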10.1 Sponsor-Investigator Reporting Requirements

10.1.1 Reporting to the Human Research Protection Office (HRPO) at Washington University

Reporting will be conducted in accordance with Washington University IRB Policies.

Pre-approval of all protocol exceptions must be obtained prior to implementing the change.

10.1.2 Reporting to Verastem

All initial and follow-up SAEs to include unanticipated problems and pregnancies, must be reported to Verastem, Inc. Safety and Pharmacovigilance via PPD at [contact] within 24 hours of knowledge of the event concerning the Verastem, Inc. product. Reports should be submitted in English via the sponsor-investigator internal SAE/pregnancy forms, MedWatch or CIOMS forms.

Pregnancy per se is not considered an AE unless there is cause to believe that the study interventions may have interfered with the effectiveness of a contraceptive medication or if the outcome of the pregnancy meets SAE criteria (miscarriage or congenital anomaly/birth defect, etc.), in which case it should be reported in the same manner and timelines as an SAE. In addition, any infant death or congenital anomaly occurring after 30 days that the Investigator suspects is related to the in-utero exposure to the study interventions should also be reported as an SAE. Hospitalization for normal delivery of a healthy newborn is not an SAE.

Since duvelisib has not been evaluated in pregnant or nursing women, the treatment of pregnant women or WCBP who are not using highly effective contraception is contraindicated.

Pregnancies occurring in subjects or partners of male subjects during the study intervention period and until 30 days after the subject's last dose of study interventions are considered immediately reportable events. If a pregnancy occurs in a subject, study interventions must be discontinued immediately. The pregnant woman should be referred to an obstetrician/gynecologist experienced in reproductive toxicity for further evaluation and counseling. The Investigator will observe the pregnant woman until completion of the pregnancy and must notify Verastem of the outcome within 24 hours of the Investigator's knowledge of the pregnancy outcome using a Pregnancy Outcome Form. This notification includes pregnancies resulting in live, "normal" births.

SAE reports must contain the following minimum information:

- At least one identifiable reporter
- One single identifiable patient
- At least one suspect adverse reaction
- At least one suspect medicinal product
- The sponsor-investigator's assessment of causality for the event

All such occurrences listed in this section shall be reported to Verastem using an approved local regulatory form and/or SAE form provided by Verastem and sent by facsimile or email to the following:

[contact]

Email: [contact]

FDA submissions of IND safety reports should be reported to the contact information provided above and reported to Verastem in the same timeframe as the submission. Copies of any correspondence or telephone conversation logs with the applicable Regulatory Authorities regarding all SAE(s), irrespective of association with the Study Drug(s), within a reasonable time frame must be provided to Verastem, Inc. Safety and Pharmacovigilance. The sponsor-investigator will provide additional information about SAEs or Safety Information upon request.

An aggregate listing of all SAEs and pregnancies reported by the site will be sent monthly by Verastem to the sponsor-investigator site for the site's reconciliation. Discrepancies between Verastem and sponsor-investigator site's records will be investigated by the sponsor-investigator site. The sponsor-investigator will send an updated SAE/pregnancy forms, MedWatch or CIOMS to Verastem or designee to resolve identified discrepancies.

